6.0 STATISTICAL ANALYSES

6.1 BASELINE DESCRIPTIVE STATISTICS

The statistical team will summarize baseline and demographic characteristics by intervention group and will apply summary statistics for both continuous and categorical variables. For continuous variables, descriptive measures will include number of non-missing values, mean, standard deviation, median, minimum, and

maximum. For categorical variables, descriptive statistics will include frequency counts and percentages by category.

Table 2: Overall descriptive summary of parent/caregiver and children characteristics

Parent/caregiver Variables	Vaccine Uptake App	General Health App	Total
Female, N (%)			
Ethnicity, N (%)			
Race, N (%)			
Rurality (self-reported), N (%)			
Insurance			
Etc....			
Children Variables			
Female, N (%)			
Ethnicity, N (%)			
Race, N (%)			
Age group, N (%)			
Etc....			

Table 3: Descriptive summary of parent/caregiver and children characteristics (by site)

Site	Vaccine Uptake App	General Health App	Total
1 Parent/caregiver Variables			
Female, N (%)			
Ethnicity, N (%)			
Race, N (%)			
Rurality (self-reported), N (%)			
Insurance			
Etc....			
1 Children Variables			
Female, N (%)			
Ethnicity, N (%)			
Race, N (%)			
Age group, N (%)			
Etc....			
Etc...			

6.2 ANALYSIS OF THE PRIMARY EFFICACY ENDPOINT

For the primary efficacy measure, we will test the following null hypothesis:

H₀: Vaccination series completion rate among children of caregivers assigned to the Vaccine Uptake app will not differ from the vaccine series completion rate among children of caregivers assigned to the General Health app

vs

H₁: Unvaccinated children of caregivers assigned to the Vaccine Uptake app will be more likely to achieve COVID-19 vaccine series completion than those children whose caregivers are assigned to the General Health app

For each vaccine-eligible child, the primary endpoint will be whether or not the child initiates and completes the COVID-19 vaccine series during the 24 weeks of the intervention period. The study team will define vaccine series completion as per the current ACIP guidance for the vaccine product. For children who receive a product that requires more than 2 doses for the primary series, receipt of up to 3 doses will be considered complete. Vaccine doses will only be valid for study purposes if given within the 24 weeks of study participation. Additional doses, when required for primary series completion, will only be valid if they are in accordance with ACIP-recommended interval minus a 4-day grace period, in accordance with recommendations of the ACIP. Also, per ACIP, there will be no maximum interval between valid doses. Incorrect second vaccine product (i.e., mixed series) will be invalid for study purposes.

Univariate Analysis

The primary endpoint will be collected as a dichotomous variable (yes/no). We will report the probability of COVID-19 vaccine series completion for each intervention group (Vaccine Uptake app vs General Health app). Initially, an unadjusted non-modeling approach using SAS PROC FREQ will be used estimate the relative risk (RR) for COVID-19 vaccine series completion (with Wald 95% CI), with the General Health app intervention group as the reference group. The analysis will be performed for all three populations (ITT, mITT, and PP).

Primary and Multivariable Analysis

A mixed-effect Poisson regression with robust error variance will be used to report adjusted relative risk (RR) with 95% CI accounting for site random effect and controlling for clustering by caregiver. The multivariable model will allow adjustment for covariates. The analysis will be performed for all three populations (ITT, mITT, and PP).

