3. STUDY OVERVIEW

3.1 STUDY DESIGN

This multi-site, parallel, randomized, controlled trial will assign parents/caregivers of children eligible to receive COVID-19 vaccine seen at participating clinics to receive either the mHealth Vaccine Uptake app or the General Health app containing general infection and child health topics. Randomization will be stratified by clinic using a permuted block design with varying block size. Outcome is receipt of COVID-19 vaccine by the parents'/caregivers' children.

Figure 1: Schema of study intervention

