3.2 RANDOMIZATION AND BLINDING

3.2.1 Randomization

The study will use a 1:1 parallel design at the caregiver level to assign caregivers to the intervention (Vaccine Uptake app) or the control (General Health app) arm. The study team will stratify randomization by participating clinic and in varying block of participants using a permuted design. Randomization will occur after enrollment and before the baseline assessment.

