Public Health Impact. In this study, we are estimating that using the Vaccine Uptake app will result in a 10% increase in the proportion of children who will complete COVID-19 vaccination. When looking at the impact of a 10% increase in pediatric vaccination rates, based on a US population of 53.7 million children 5-17 years of age,⁶ such an increase would result in an additional 5 million vaccinated children. Previous research has shown that app-based vaccine uptake interventions are less costly than more traditional methods, such as paper handouts and communication tools. We estimate a cost of \$10,000 dollars for the first year of a customized version of the

Vaccine Uptake app per state. Deployment of the Vaccine Uptake app nationally would cost a little as \$500,000 dollars per year, or 10 cents per additional child who completes COVID-19 vaccination.

In determining sample size, each caregiver is considered to be a cluster with an average of 2 unvaccinated children. To demonstrate an improvement in the proportion of unvaccinated children of caregivers who complete the COVID-19 vaccination series due to the mHealth intervention from 30% to 40%^{7,8,9} would require 758 caregivers (379 per arm), at the two-sided 0.05 significance level with power of 0.90 and an intraclass correlation coefficient of 0.60. The table below shows the sample size needed to have 90% power to detect a 10-percentage point increase in the proportion of children who complete the vaccination series using the Vaccine Uptake app with varying levels of intraclass correlation. To ensure that there are at least 758 caregivers, the primary analysis population, we expect to randomize 892 caregivers to account for up to 15% of randomized participants who do not use the Vaccine Uptake app or General Health app after downloading it during enrollment.

Intraclass Correlation Coefficient	Sample Size
0.40	331 per arm (662 total)
0.50	355 per arm (710 total)
0.60	379 per arm (758 total)
0.70	402 per arm (804 total)
0.80	426 per arm (852 total)

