6.3 ANALYSIS OF THE SECONDARY EFFICACY ENDPOINT(S)

6.3.1 Vaccine Series Initiation

For the secondary efficacy measure, we will test the following null hypothesis:

H₀: Vaccination series initiation rate among children of caregivers assigned to the Vaccine Uptake app will not differ from the vaccine series initiation rate among children of caregivers assigned to the General Health app

vs

H₁: Unvaccinated children of caregivers assigned to the Vaccine Uptake app will be more likely to achieve COVID-19 vaccine series initiation than those children whose caregivers are assigned to the General Health app

For each vaccine-eligible child, this secondary endpoint will be defined as whether or not the child initiates the COVID-19 vaccine series during the 16 weeks of study participation. Vaccine series initiation will be receipt of at least 1 valid dose of any COVID-19 vaccine product. Vaccine doses for series initiation will only be valid for study purposes if given within the 16 weeks of study participation.

Univariate Analysis

The secondary vaccine series initiation endpoint will be collected as a dichotomous variable (yes/no). We will report the probability of COVID-19 vaccine series initiation for each intervention group (Vaccine Uptake app vs General Health app). Initially, an unadjusted non-modeling approach using SAS PROC FREQ will be used estimate the relative risk (RR) for COVID-19 vaccine series initiation (with Wald 95% CI), with the General Health app intervention group as the reference group. The analysis will be performed for all three populations (ITT, mITT, and PP).

Secondary and Multivariable Analysis

A mixed-effect Poisson regression with robust error variance will be used to report adjusted relative risk (RR) with 95% CI accounting for site random effect and controlling for clustering by caregiver. The multivariable model will allow adjustment for covariates. The analysis will be performed for all three populations (ITT, mITT, and PP).

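### The unadjusted relative-risk interval for completion (SAP 6.2) ignores clustering by caregiver, so its nominal 95% CI covers about 88%; the main models are not affected

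*SAP*

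**What the plan says.** The unit of randomization is the caregiver (SAP 3.2.1): "The study will use a 1:1 parallel design at the caregiver level to assign caregivers to the intervention". The unit of the endpoint is the child: SAP 6.2 defines completion for every eligible child.

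The plan knows that the two differ. In SAP 3.3, "each caregiver is considered to be a cluster with an average of 2 unvaccinated children", and the sample size is set at the "two-sided 0.05 significance level with power of 0.90 and an intraclass correlation coefficient of 0.60". The main model in SAP 6.2 gives an "adjusted relative risk (RR) with 95% CI accounting for site random effect and controlling for clustering by caregiver".

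The step that precedes that model, under the sub-heading Univariate Analysis, has no caregiver term. It gives the completion probability in each arm and then an "unadjusted non-modeling approach using SAS PROC FREQ will be used estimate the relative risk (RR) for COVID-19 vaccine series completion (with Wald 95% CI". SAP 6.3.1 has the parallel sentence for the secondary endpoint: "unadjusted non-modeling approach using SAS PROC FREQ will be used estimate the relative risk (RR) for COVID-19 vaccine series initiation (with Wald 95% CI". Each step is to be run in the ITT, mITT and PP populations, which makes six intervals before any subgroup analysis. SAP 5.2 states that every confidence interval presented will be at the 95% level.

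**The concern.** A PROC FREQ Wald interval for a relative risk is valid when the rows of the table are independent. Here the rows are children, and children of one caregiver share one allocation and, by the plan's own assumption, strongly correlated outcomes. The variance is therefore too small and the interval too narrow. The SAP does not reduce the data to one record per caregiver for this step, and no other section corrects the variance.

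What is at stake is reporting. The results would probably carry two 95% intervals for the same comparison, one of which overstates precision. The trial's conclusion does not hang on it, because the model that serves for inference controls for clustering.

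**Working it through.** **Inputs (SAP 3.3).** Completion 30% vs 40%; two-sided alpha 0.05; power 0.90; mean of m = 2 children per caregiver; intraclass correlation (ICC) 0.60, tabulated from 0.40 to 0.80; 892 caregivers randomized, so 446 per arm and 892 children per arm.

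**The plan's own sample size.** Children per arm with unpooled variance: (1.960 + 1.282)² × (0.30×0.70 + 0.40×0.60) / 0.10² = 472.83. The design effect is DE = 1 + (m − 1) × ICC = 1 + 0.60 = 1.6. Caregivers per arm: 472.83 × 1.6 / 2 = 378.27, rounded up to 379, as stated. The same formula returns all five rows of the ICC table (331, 355, 379, 402, 426), and 758 / 0.85 = 891.8 gives 892. So the plan's sample size already uses the design effect that the PROC FREQ interval omits.

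**Coverage of the uncorrected interval.** The true standard error is √DE times the PROC FREQ one, so coverage = 2Φ(1.96/√DE) − 1. With exactly 2 children per caregiver:

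| ICC | DE | Coverage |
|---|---|---|
| 0.40 | 1.4 | 90.2% |
| 0.50 | 1.5 | 89.0% |
| 0.60 | 1.6 | 87.9% |
| 0.70 | 1.7 | 86.7% |
| 0.80 | 1.8 | 85.6% |

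At ICC 0.60, √1.6 = 1.265 and 1 − 1/1.265 = 0.21, so the interval is 21% too narrow on the log scale. With no true effect it would exclude RR = 1 in 12.1% of trials instead of 5%.

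**Unequal family sizes.** The plan gives 2 only as an average. With coefficient of variation CV, DE = 1 + ((1 + CV²) × m − 1) × ICC. Both distributions below are assumptions with mean 2:

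| Children per caregiver | CV | DE at ICC 0.60 | Coverage at ICC 0.60 | Coverage, ICC 0.40 to 0.80 |
|---|---|---|---|---|
| 1, 2, 3 (25/50/25%) | 0.354 | 1.75 | 86.2% | 89.1% to 83.4% |
| 1, 2, 3, 4 (40/30/20/10%) | 0.50 | 1.90 | 84.5% | 87.9% to 81.4% |

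**Simulation.** Beta-binomial outcomes, ICC 0.60, 20,000 replicates per setting. With exactly 2 children, the uncorrected interval covered 87.7% to 88.2% (379 or 446 caregivers per arm; 30% in both arms, or 30% vs 40%). A caregiver-robust interval, at 446 per arm, covered 95.1% to 95.2%. Under the two assumed family-size distributions the uncorrected interval covered 84.3% to 86.2%, and the robust one 94.7% to 95.3%.

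**What a reader would see.**

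- At 30% vs 40% with 892 children per arm, SE(log RR) = √(0.7/(0.3×892) + 0.6/(0.4×892)) = 0.0656 uncorrected, and 0.0656 × 1.265 = 0.083 clustered. For RR 1.33 the intervals are 1.173 to 1.516 and 1.133 to 1.569. Both exclude 1.
- At an observed 30% vs 35% (RR 1.17) they are 1.020 to 1.334 and 0.984 to 1.383, which disagree about 1. Against 30%, disagreement occurs for observed intervention rates from about 34.4% to 35.5%.

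**The case against.** The strongest case against concerns materiality. The step is labelled preliminary and unadjusted, has no test or decision rule, and is followed at once by the model that the SAP names as primary. A crude relative risk ahead of the modelled one is ordinary descriptive reporting. All of that stands, and it is why the point is minor. It does not rescue the interval, because the word unadjusted speaks of covariates: a 95% interval without covariates still needs a variance that respects the randomized unit.

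The 88% is also conditional. The ICC of 0.60 is a planning assumption; at an assumed 0.20 with 2 children per caregiver the same formula gives about 93%. This stands too. The range that rests on the plan's own inputs, taking exactly 2 children for every caregiver, is 85.6% to 90.2%; the lower figures depend on assumed family sizes.

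Publication of both intervals is an inference. The SAP attaches the word report to the arm probabilities and to the adjusted RR, and says only that the PROC FREQ RR will be estimated. SAP 5.2 nevertheless promises 95% for any interval presented.

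Finally, the two-by-two table also ignores the design feature in SAP 3.1 that "Randomization will be stratified by clinic using a permuted block design with varying block size". Ignoring stratification could offset the under-coverage a little, but the documents give no clinic-level correlation from which to say how much.

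**Conclusion.** The concern holds, as a minor point. As written, the unadjusted 95% interval for completion covers about 88% under the plan's own assumptions, and probably less if family sizes vary. The figure rests on three things: the table is built on child records, which follows from the child-level endpoint; every caregiver has 2 children; and the ICC is 0.60. For initiation the method has the same fault, but its size is unknown because the plan gives no ICC for that endpoint; carrying the completion figures over would be an assumption.

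The relative-risk estimate itself is not in question. The main models for completion and initiation and the sample size are unaffected, and at the plan's alternative both intervals lead to the same reading.

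**What to change.** Amend the Univariate Analysis paragraphs of SAP 6.2 and 6.3.1 in one of two ways:

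- Compute the unadjusted RR interval with a robust variance clustered by caregiver, for example a modified Poisson model fitted by GEE with intervention arm as the only term, caregiver as the cluster and an independence working correlation. This keeps the simple ratio of the two arm proportions as the estimate.
- Drop the interval and keep only the descriptive result already planned there: "We will report the probability of COVID-19 vaccine series completion for each intervention group", and likewise for initiation.

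If the PROC FREQ interval is retained, the least change is to label it as not corrected for clustering by caregiver. That tells the reader about the under-coverage but leaves it in place.

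The cost is a few lines of SAP text and code, with no new data and no protocol amendment. The unadjusted interval becomes about 26% wider on the log scale with exactly 2 children per caregiver (√1.6 = 1.265), or 32% to 38% wider under the assumed family sizes (√1.75 = 1.323, √1.90 = 1.378). That is the width the data support.

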## 1. PROTOCOL SUMMARY

### 1.1 SYNOPSIS

Title:	Improving pediatric COVID-19 vaccine uptake using an mHealth tool: a randomized, controlled trial	
Study Description:	Site-level block-randomized trial	
Objectives:	Primary Objective:	Determine the effect of a parent-facing, vaccination decision-making mobile health (mHealth) tool on children's COVID-19 vaccine series completion
	Secondary Objective 1:	Determine the effect of a parent-facing, vaccination decision-making mHealth tool on children's COVID-19 vaccine series initiation
	Secondary Objective 2:	Determine the effect of a parent-facing, vaccination decision-making mHealth tool on parental attitude toward pediatric COVID-19 vaccination
Endpoints:	Primary Endpoint:	Proportion of children who complete COVID-19 vaccination, as verified in state, clinic, or participant-held records

**Secondary Endpoint 1:** Proportion of children who receive ≥1 dose of the COVID-19 vaccination series, as verified in state, clinic, or participant-held records

**Secondary Endpoint 2:** Change in enrolled parent/caregiver domain scores from baseline to immediately post-intervention on the modified WHO SAGE Vaccine Hesitancy Scale adapted for the COVID-19 Vaccine

**Study Population:** Custodial parents/caregivers with  $\geq 1$  child eligible for COVID-19 vaccination who has not yet received the vaccine at the time of study enrollment.

**Phase:** N/A

**Description of Sites/Facilities Enrolling Participants:** Enrolling sites will recruit participants. These sites will collaborate with outpatient practices within ECHO ISPCTN states that provide primary care services to children (<18 years old). Sites will serve a population base of at least 40% Medicaid/uninsured children, <60% non-Hispanic White children, or >40% of families residing in rural communities. Sites are encouraged, but not required, to have a high Spanish-speaking population.

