## 5. STUDY DESIGN

### 5.1 OVERALL DESIGN

This multi-site, parallel, randomized, controlled trial will assign parents/caregivers of children eligible to receive COVID-19 vaccine seen at participating clinics to receive either the mHealth Vaccine Uptake app or the General Health app containing general infection and child health topics. Randomization will be stratified by site using a permuted block design with varying block size. Outcome is receipt of COVID-19 vaccine by the parents'/caregivers' children.

[figure not shown]

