### 7.5.2 APP REGISTRATION AND USAGE (ADHERENCE)

During enrollment, site coordinators/research team members will ask participants if they would like assistance downloading and registering with the app. If participants request assistance, they will be scheduled with a Research Team member for technical assistance. After enrollment, caregiver participants will be block-randomized within their participating clinic by the enrolling site to either the Vaccine Uptake or General Health app study arms (see Section 8.2 for complete details on randomization). A Research Team member will then register the caregiver in the assigned app using their assigned study number as well as the caregiver participant's self-identified race, ethnicity, gender identity, rurality, and clinic of recruitment collected at enrollment. The Research Team will send caregiver participants the instructions on how to download their assigned app. Once downloaded, participants will enter their email address to retrieve their registration. The Research Team will follow up with participants who have not used the app within one week of registration/instructions successfully sent via telephone, email, or video conference to confirm the completion of app registration. Each time the app is opened, every selection made within the app will be tagged and recorded with both the caregiver participant's study number and a time date stamp. This data will be tracked throughout the caregiver participant's 24-week intervention to determine adherence (Section 8.3).

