## 8.3 MEASURES TO MINIMIZE BIAS: RANDOMIZATION

**Randomization:** The study will use a 1:1 parallel design at the caregiver level to assign caregivers to the intervention (Vaccine Uptake app) or the control (General Health app) arm. The study team will stratify randomization by participating clinic and in varying block of participants using a permuted design. Randomization will occur after enrollment and before the baseline assessment.

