### 11.4.2 ANALYSIS OF THE PRIMARY EFFICACY ENDPOINT(S)

**COVID-19 Vaccine Series Completion.** For each vaccine-eligible child, the primary endpoint will be whether or not the child initiates and completes the COVID-19 vaccine series during the 24 weeks of the intervention period. The study team will define vaccine series completion as per the current ACIP guidance for the vaccine product. For children who receive a product that requires more than 2 doses for the primary series, receipt of up to 3 doses will be considered complete. Vaccine doses will only be valid for study purposes if given within the 24 weeks of study participation. Additional doses, when required for primary series completion, will only be valid if they are in accordance with ACIP-recommended interval minus a 4-day grace period, in accordance with recommendations of the ACIP. Also, per ACIP, there will be no maximum interval between valid doses. Incorrect second vaccine product (i.e., mixed series) will be invalid for study purposes. The statistical team will use a mixed model with the binomial distribution and the logit link to compare the two intervention groups with respect to the proportions of children who complete COVID-19 vaccination, using a site random effect and controlling for clustering by caregiver.

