6.3.2 Parental Attitude Toward Pediatric COVID-19 Vaccination

The study team will evaluate parental attitude toward pediatric COVID-19 vaccination by using the modified SAGE Vaccine Hesitancy Scale that includes ten statements with ordinal responses using a 5-point Likert scale. At baseline and week 16, the study statisticians will generate summary statistics and graphical display for each of the 10 questions for the two intervention groups.

Analysis for SAGE Vaccine Hesitancy Scale Items

For each item, the study statisticians will report response frequency overall and by intervention groups. A mean score chi-square test (i.e., test of location shift) will be used to examine the association between responses and intervention groups. For the adjusted analysis, a linear mixed model will be used to account for parent/caregivers nested within clinics and allow adjustment for covariates. The analysis will be performed for all three populations (ITT, mITT, and PP).

Analysis for SAGE Vaccine Hesitancy Scale Composite

A composite vaccine hesitancy score will be the sum of the 10 items/statements after reverse coding items 1, 2, 3, 4, 6, 7, and 8 (range of 10 to 50). The study statisticians will provide summary statistics including means and standard deviation at baseline and week 16. A linear mixed model will be used to account for parent/caregivers nested within clinics and allow adjustment for covariates. The analysis team will report point estimates for the intervention group mean difference along with 95% CI. The analysis will be performed for all three populations (ITT, mITT, and PP).

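### Randomisation is stratified by participating clinic, but the completion and initiation models carry only a site effect, and two protocol passages name site as the randomisation level; the cost is a slightly over-wide confidence interval

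*SAP*

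**What the plan says.** **Level of randomisation.** Four places put it at the clinic.
- Protocol 8.3: "The study team will stratify randomization by participating clinic and in varying block of participants using a permuted design". SAP 3.2.1 carries the same text.
- Protocol 7.5.2: caregivers are "block-randomized within their participating clinic by the enrolling site".
- SAP 3.1: "Randomization will be stratified by clinic using a permuted block design with varying block size".

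Two places put it at the site.
- Protocol 5.1: "Randomization will be stratified by site using a permuted block design with varying block size".
- Protocol synopsis (1.1): "Site-level block-randomized trial".

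**Site and clinic are different units.** The protocol's definitions section separates the enrolling site (where participants are screened and consented) from the participating clinic (the institution that supplies potential participants). Protocol 7.1 plans 15 enrolling sites with about two clinics each, and also states a goal of 24 clinics.

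**Analysis models.**
- Completion, protocol 11.4.2: a logit mixed model "using a site random effect and controlling for clustering by caregiver". Completion, SAP 6.2: a Poisson mixed model that "will be used to report adjusted relative risk (RR) with 95% CI accounting for site random effect and controlling for clustering by caregiver".
- Initiation, protocol 11.4.3 and SAP 6.3.1: the same terms as the corresponding completion model.
- Hesitancy, SAP 6.3.2: "a linear mixed model will be used to account for parent/caregivers nested within clinics and allow adjustment for covariates". Protocol 11.4.3 uses site for this endpoint.

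The SAP lets covariates into the completion and initiation models but names none.

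**The concern.** When allocation is balanced within strata, chance differences between strata cannot enter the treatment comparison. An analysis gets full credit for that only if the model also removes the between-stratum variation. Here the stratum is the clinic. The primary and first secondary models remove variation between sites but leave variation between clinics of one site in the error term. Such variation is plausible: under protocol 6.1.2 a clinic qualifies on any one of three patient-mix criteria (race and ethnicity, rurality, payer), and stocking the vaccine is not required.

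Three things are at stake, all modest: a standard error that is a little too large; a report that cannot state one stratification factor without contradicting part of the protocol; and, in an unmasked trial whose primary model admits unnamed covariates, a choice about clinic left open on the primary endpoint.

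**Working it through.** **1. Reproduce the plan's sample size.** Inputs (SAP 3.3, protocol 11.2): 30% versus 40%, two-sided 0.05, power 0.90, 2 children per caregiver, caregiver ICC 0.60.

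- Children per arm: (1.960 + 1.282)² × (0.3×0.7 + 0.4×0.6) / 0.10² = 472.8
- Design effect: 1 + (2 − 1)×0.60 = 1.6
- Caregivers per arm: 472.8 × 1.6 / 2 = 378.3, rounded up to 379 (758 in total)
- Randomised: 758 / 0.85 = 891.8, rounded up to 892

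All stated figures reproduce, as does the whole ICC table (331, 355, 379, 402, 426).

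**2. Variance with and without the stratum.** In units of p(1−p), a caregiver mean has variance (1 + 0.60)/2 = 0.8. Let ρ be the share of child-level variance due to clinic within site. The documents do not give it, so 0.02, 0.05 and 0.10 are assumed. With two equal clinics per site, the site term absorbs about half of ρ.

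- Site-only model: 0.8 − ρ/2
- Clinic model: 0.8 − ρ
- SE ratio = √[(0.8 − ρ/2)/(0.8 − ρ)]
- Equivalent caregivers = 892 × [(0.8 − ρ/2)/(0.8 − ρ) − 1]
- Power = Φ(0.10/SE − 1.96), with SE = √(0.45 × variance / 379)

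| ρ | Variance ratio | SE excess | Caregivers on 892 | Power, site only | Power, clinic |
|---|---|---|---|---|---|
| 0 | 1 | 0% | 0 | 90.1% | 90.1% |
| 0.02 | 0.790/0.780 | 0.6% | 11 | 90.4% | 90.8% |
| 0.05 | 0.775/0.750 | 1.7% | 30 | 90.9% | 91.8% |
| 0.10 | 0.750/0.700 | 3.5% | 64 | 91.8% | 93.4% |

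The power difference is about 0.4, 0.9 and 1.6 points.

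**3. What kind of loss this is.** The site-only column treats the larger SE as the true spread of the estimate. Under clinic-stratified allocation the true spread is close to the clinic SE, so site-only power is better written Φ[(0.10 − 1.96×SE_site)/SE_clinic]. At ρ = 0.10, SE_site = 0.02984 and SE_clinic = 0.02883, giving Φ(1.44) = 92.5% against 93.4%. The same step gives 90.6% against 90.8% at ρ = 0.02 and 91.3% against 91.8% at 0.05. The figures of 0.4 to 1.6 points are therefore an upper reading; 0.2 to 0.9 is closer.

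**4. Simulation check.** Clinic-stratified permuted blocks, 15 sites × 2 clinics × 25 caregivers, 4,000 runs per scenario, risk-difference model.

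| Clinic-within-site ICC | Reported SE, site / clinic | Spread of estimates, site / clinic | Power, site / clinic | Type I error, site / clinic |
|---|---|---|---|---|
| 0.044 | 0.0304 / 0.0300 | 0.0300 / 0.0300 | 91.2% / 91.5% | 4.2% / 4.7% |
| 0.099 | 0.0302 / 0.0292 | 0.0291 / 0.0291 | 90.7% / 91.6% | 4.4% / 5.3% |

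The estimates are as precise under either model. Only the reported SE differs, by 1.4% and 3.3%. With 4,000 runs the Monte Carlo error on a 5% rate is about 0.3 points (√(0.05×0.95/4000)), so 5.3% is compatible with the nominal level.

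**The case against.** **Site may simply mean clinic.** Protocol 6.1.2 is headed as criteria for sites but lists criteria for participating clinics, and the protocol uses site for hesitancy where the SAP uses clinics. If the words are interchangeable, there is no modelling error. Part of this stands: usage is loose. But the definitions section separates the units, protocol 7.1 counts clinics per site, and the SAP uses site in 6.2 and clinics in 6.3.2. If clinic was meant throughout, the models still need to say so.

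**The effect is small and rests on an assumed ICC.** This stands in full. A reader might infer twice the cost: an SE excess of 1.3%, 3.3% or 6.9%, or 23, 59 or 127 caregivers at the same three ICCs. Those figures require the site term to absorb none of the clinic variance, which does not fit a model with a site effect and about two clinics per site. The goal of 24 clinics over 15 sites averages 1.6 per site, so some sites may have only one clinic, where site and clinic coincide.

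**The analysis does not fail.** Also correct. A reader might infer bias, false positives or an underpowered trial. None follows: the error is in the conservative direction, and calculated power with site only stays at or above 90% at 758.

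**Randomisation is already settled as clinic-level.** Largely fair. The operational text and the randomisation section both say clinic, and SAP 3.1 has clinic where protocol 5.1 has site. A reader might infer that some sites randomised across clinics, or take the synopsis label as cluster randomisation by site. Nothing suggests the former, and protocol 8.3 assigns at caregiver level. The wording conflict remains.

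**Clinic could enter as a covariate.** It could, but it is not pre-specified.

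**Conclusion.** The point holds as a minor mismatch between design and analysis, plus a wording conflict. The conflict and the missing clinic term are certain from the text, subject to reading site as the protocol defines it. The numerical cost is conditional: it assumes a clinic-within-site ICC of 0.02 to 0.10, two equal clinics per site, 2 children per caregiver and caregiver ICC 0.60. On those terms the reported SE is 0.6% to 3.5% too large, worth about 11 to 64 caregivers on 892 and at most about 0.4 to 1.6 power points. It falls to zero where clinics within a site do not differ or a site has one clinic. The arithmetic and simulation are on the risk-difference scale; they indicate the order of size for the SAP's relative-risk model and are not an exact figure for it.

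**What to change.** - In SAP 6.2 and 6.3.1 and protocol 11.4.2 and 11.4.3, specify participating clinic, either alone or nested in site, in place of site only. State in advance that very small clinics are pooled within their site if the model does not converge, and set the size threshold before outcome data are seen.
- In protocol 5.1 and the synopsis, describe randomisation as stratified by participating clinic.
- If the sponsor already means clinic wherever these models say site, write clinic there.

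The cost is wording only. Clinic of recruitment is collected at enrollment (protocol 7.5.2), the SAP hesitancy models already use clinic, and the sample size does not change.
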